# **Feasibility and Specificity of BinaxNOW for Diagnosis and Surveillance of Infection with SARS-CoV-2 in Schoolchildren**

**UW-Madison Health Sciences IRB #2020-1521**

**ClinicalTrials.gov NCT05087524**

**Protocol Version 2.0, March 4, 2021**

## **A. Background**

The Coronavirus Disease 2019 (COVID-19), caused by the SARS-CoV-2 virus, is a worldwide pandemic that has resulted in large scale quarantines in cities, states and countries throughout the world. SARS-CoV-2 is a respiratory virus that is most commonly spread via contact with infective respiratory droplets and aerosols produced by coughing, sneezing, talking, and singing. Daycare centers and schools are known to be locations with high burdens of viral respiratory tract infections associated with horizontal transmission of infection to the children, teachers and their attendants. The role which children in daycare centers and schools play in the transmission of COVID-19 to each other as well as their parents and day care workers is unknown. Furthermore, the most effective strategies to limit those infections and thereby maintain children and their teachers/daycare workers within their educational setting and their parents at their place of employment have not been studied.

**Disparities in health outcomes.** Disparities in health outcomes to COVID-19 in minority populations have become evident in the United States. The burden of disease, both morbidity and mortality, experienced by Hispanics and Blacks has far exceeded their proportion in the general population. The CDC and other groups report that there are more COVID-19 cases, hospitalizations, and deaths in areas where racial and ethnic minority groups live and that community strategies to slow the spread of COVID-19 may cause unintentional harm, such as lost wages, reduced access to services, and increased stress for some racial and ethnic minority groups

**Role of School Children.** In most early investigations, the source of family outbreaks has been the adult members of the household. However, schools/daycares were closed very early as a reflexive response to the pandemic in most locations. Accordingly, the question regarding children has been, in large part, whether they will be a source of infection for each

other, their parents, teachers and daycare workers, therefore exerting a multiplier effect on the proportions of the pandemic.

**The two-fold importance of daycare and school attendance.** The importance of the availability of school and daycare to the ability to re-open the economy cannot be overemphasized. A substantial portion of the front-line work force, including both health care personnel and other essential workers, have families with children of school or pre-school age. Furthermore, the contributions of school attendance to the overall well-being of the physical and mental health of children in addition to their nutrition, guidance, emotional support, socialization and education is universally recognized.

**Current strategies for prevention of infection in schools.** Current strategies for the prevention of infection both in and outside of schools have included physical distancing, use of face masks, frequent handwashing and self-exclusion at the sign/symptoms of even minor illness. One of the difficulties imposed by infection with SARS-CoV-2 has been the consistent demonstration that transmission of infection precedes the development of symptoms, thereby allowing the “silent” transmission of infection in most cases even before the onset of symptoms. In addition, many children infected by SARS-CoV-2 are completely asymptomatic but nevertheless very effectively transmit the virus. Therefore, the key to maintaining attendance at school and daycare is **rapid identification of both symptomatic and asymptomatic children, teachers and other school staff for exclusion.** Many respiratory infections in the coming respiratory season will not be caused by SARS-CoV-2 but rather by other common respiratory viruses. Therefore, prompt diagnostic testing will be the key to documenting that children with mild respiratory symptoms, usually not qualifying for exclusion from school, actually do NOT have SARS-CoV-2 but rather another more benign respiratory viral infection.

**BinaxNOW Covid-19 Ag Card.** The means to rapidly identify and exclude symptomatic and asymptomatic children, teachers and other school staff from the classroom is potentially available as a rapid, easy to perform, relatively inexpensive test called BinaxNOW Covid-19 Ag Card manufactured by Abbott. The Food and Drug Administration (FDA) has

granted emergency use authorization for this test. We are requesting a Non-Significant Risk determination from the IRB for its use in this study, which is going to be outside of the EUA's indications. It works with a nasal swab sample and a credit card sized reactive card to detect the nucleocapsid protein antigen from SARS-CoV-2 (using a lateral flow assay) and results are available in 15 minutes. The emergency use authorization is for use of the BinaxNow Covid-19 card for symptomatic adult patients within 7 days of the onset of their illness. There is very good reason to believe that this technology will be effective in creating "safe schools", however, there are no data to prove that. The 'cards' have been reported to be reasonably sensitive (85 to 95% as sensitive as polymerase chain assays for the spike protein of the virus) but have not been tested in children or broadly in the US. Accordingly, we are proposing a **two-step** investigation to establish the effectiveness of a strategy built on the availability of both diagnostic testing of symptomatic individuals and screening twice weekly of asymptomatic children and teachers. In step 1, we will demonstrate the feasibility and specificity of using BinaxNOW in school children and their teachers. In step 2, we will demonstrate the effectiveness of this strategy in maximizing school/work attendance for children and families receiving this intervention compared to students and teachers for whom this intervention is not available.

## **Purpose and Research Goal**

The overall purpose and research goal of this project is to understand how the virus SARS-CoV-2 is spread in the K-8 setting, decrease secondary cases of COVID-19, improve attendance and educational opportunities for children, teachers and other school staff, and decrease time away from work for parents (with threat of loss of employment and other benefits).

### **Inclusion Criteria:**

- Children aged 5 - 15 years inclusive
- Currently attending school K-8 at one of the designated schools of the Madison Metropolitan School District
- Teachers and other school staff aged 20-65 years

### **Exclusion Criteria:**

- Children < 5 years or  $\geq$  16 years
- Teachers and other school staff < 20 years or > 65 years

We hypothesize that prompt diagnostic testing for SARS-CoV-2 in symptomatic children and twice weekly surveillance of asymptomatic children (with appropriate exclusion of children with positive tests) will be effective as a strategy to achieve maximum attendance in school and minimal disruption of the associated workforce.

**STEP 1:** Determine feasibility of using BinaxNOW COVID19 cards for diagnosis and surveillance of infection with SARS-CoV-2 in teachers, other school staff, and school children.

The specific aims are to determine:

- a. if it is feasible to obtain nasal samples to be used with the BinaxNOW COVID-19 for diagnosis of COVID-19 in children or teachers/other school staff with symptoms compatible with a diagnosis of COVID-19.
- b. if it is feasible to obtain nasal samples twice weekly to be used with BinaxNOW COVID-19 for surveillance of infection with SARS-CoV-2.
- c. The specificity of positive tests for SARS-CoV-2 obtained for diagnosis or surveillance compared to traditional PCR diagnostic testing.

**STEP 2:** Determine effectiveness of prompt diagnostic testing and twice weekly surveillance for SARS-CoV-2 among children and school faculty/staff to reduce the rate of positive cases (symptomatic) of COVID-19 in an elementary school setting resulting in an ultimate decrease in absenteeism for students and an increase in attendance for their parents at the workplace.

We propose to implement STEP 1 now as a pilot study and STEP 2 at a later date.

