#### **B. Methods for STEP 1.**

240 students and 80 teachers/other school staff will be recruited from schools within the Madison Metropolitan School District. The schools will email families and teachers a letter explaining the study and inviting them to participate in a virtual information session which

includes a question answer opportunity. The virtual information sessions will describe the process of sample collection so that students and teachers know what to expect. If parents, teachers and other school staff are interested in enrolling in the study, they can contact the school at which time they will be asked if they agree to have study staff contact them. Research personnel will not directly contact parents, students, teachers or other school staff regarding initial recruitment for the study. All subjects will agree to the performance of nasal swabs samples to be used for diagnosis or screening. Samples will be obtained by research staff in the school setting. The Madison Metropolitan School District has obtained a CLIA waiver for collection of samples. When there is a positive test, a saliva sample will be collected for testing with a standard PCR method. The standard PCR samples will be processed at UW Clinical Laboratory.

All subjects will be followed for 8 weeks. Children and staff will not receive compensation for their participation in the study. Subjects are free to withdraw from the study at any time.

At the conclusion of this portion of the study, we will understand the feasibility and specificity of the testing procedures.

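### Aim c asks for the specificity of positive tests with PCR done only on positives; as worded this gives a positive predictive value, not the specificity the protocol promises

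*Protocol*

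**What the plan says.** The title is "Feasibility and Specificity of BinaxNOW for Diagnosis and Surveillance of Infection with SARS-CoV-2 in Schoolchildren". The Background, in the paragraph on the BinaxNOW card, says: "In step 1, we will demonstrate the feasibility and specificity of using BinaxNOW in school children and their teachers". Section B, Methods for STEP 1, closes with: "At the conclusion of this portion of the study, we will understand the feasibility and specificity of the testing procedures".

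The quantity is set out in one place only, specific aim c of STEP 1: "The specificity of positive tests for SARS-CoV-2 obtained for diagnosis or surveillance compared to traditional PCR diagnostic testing".

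The reference test is governed by one sentence in section B: "When there is a positive test, a saliva sample will be collected for testing with a standard PCR method". The section on reporting of test results covers who is told what, and adds no PCR for card-negative subjects. The protocol gives no formula or denominator for specificity and does not say how card-negative tests without PCR are to be counted.

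**The concern.** Specificity is the proportion of uninfected tests that the card calls negative, TN/(TN + FP). It conditions on the PCR result. Aim c conditions on the card result instead: it takes the positive tests and compares them with PCR. What PCR-tested positives can show is the proportion confirmed, TP/(TP + FP), which is the PPV.

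The difference matters because specificity is in the title, is one of three Step 1 aims and is part of the stated conclusion of Step 1. If aim c is analysed as worded, a PPV is reported under the name of specificity. A highly specific card used for screening at low prevalence would then appear to perform poorly. The figure would also move with local prevalence and with the mix of symptomatic and surveillance tests, which aim c pools.

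**Working it through.** The protocol states no expected specificity, precision target or derivation of its sample size, so there is no figure of its own to reproduce. The check uses the definitions of the two-by-two table.

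**Inputs from the protocol**
- Subjects: 240 + 80 = 320 (Methods for STEP 1).
- Surveillance twice weekly (aim b), follow-up 8 weeks (Methods for STEP 1). Scheduled surveillance swabs are at most N = 320 × 2 × 8 = 5,120; symptomatic tests come on top.
- Sensitivity relative to PCR: 85–95% (Background).

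**Assumptions, not in the protocol**
- True specificity 99% unless stated otherwise.
- Prevalence per surveillance test 0.1–2%; per symptomatic test 5–20%.

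**Step 1: which cells PCR fills.** With PCR only after a positive card, TP and FP are known. Card negatives are counted but not split into TN and FN. Specificity computed literally within the PCR-tested set is 0/(0 + FP) = 0 whenever there is any false positive. The only informative ratio in that set is the PPV.

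**Step 2: how the PPV behaves.** TP = N × prevalence × sensitivity; FP = N × (1 − prevalence) × (1 − specificity); PPV = TP/(TP + FP).

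At 0.5% prevalence:
- TP = 5,120 × 0.005 × 0.85 = 21.8, or 24.3 at 95% sensitivity.
- FP = 5,120 × 0.995 × 0.01 = 50.9.
- PPV = 21.8/72.7 = 29.9%, or 24.3/75.3 = 32.3%.

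| Tests | Assumed prevalence | PPV at 85% sensitivity | PPV at 95% sensitivity |
|---|---|---|---|
| Surveillance | 0.1% | 7.8% | 8.7% |
| Surveillance | 0.5% | 29.9% | 32.3% |
| Surveillance | 1% | 46.2% | 49.0% |
| Surveillance | 2% | 63.4% | 66.0% |
| Symptomatic | 5% | 81.7% | 83.3% |
| Symptomatic | 10% | 90.4% | 91.3% |
| Symptomatic | 20% | 95.5% | 96.0% |

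True specificity is 99% in every row. Attendance does not alter the result: at 70% (3,584 swabs, 85% sensitivity) TP = 15.2, FP = 35.7 and the PPV is still 29.9%. The pattern does not hinge on 99% either: at 99.5% specificity and 85% sensitivity the PPV runs from 14.5% at 0.1% prevalence to 89.9% at 5%.

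**Step 3: whether the data can still yield specificity.** Count every unverified card negative as PCR-negative. The estimate is 1 − FP/(N − TP), where N − TP is the false positives plus all card negatives.
- Prevalence 2%, sensitivity 85%, specificity 98%: per test, FP = 0.98 × 0.02 = 0.0196 and TP = 0.017, so 1 − 0.0196/0.983 = 98.006%, an error of 0.006 percentage points.
- The same with sensitivity 50%: 1 − 0.0196/0.990 = 98.020%, an error of 0.020 points.

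These are the largest errors over prevalence 0.1–2% and specificity 98–99.8%. The error is always upward.

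**Step 4: bound for hidden false negatives.** With FP = 51 and TP = 22, specificity is 1 − 51/(5,120 − 22 − FN). For FN = 0, 50 and 256 this gives 99.00%, 98.99% and 98.95%.

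**The case against.** The strongest reply is that aim c is awkwardly phrased, not wrong. It gives no formula and does not mention predictive value, and its literal reading (zero whenever there is a false positive) is one nobody would intend. Read with the title, Background and Methods, it could simply mean that positives are checked by PCR to find the false positives, which are the numerator of 1 − specificity. On that reading the design is sound for a low-prevalence pilot, and the denominator, clustering and handling of negatives can be left to a SAP that is not at hand. The harm is also conditional on an analysis we cannot see, and the large swings rest on assumed prevalences.

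Much of this stands. The design is adequate, the intention may well have been ordinary specificity, and interval methods belong in the SAP. But aim c is the protocol's only description of a quantity named in its title. It attaches the word specificity to positive tests, and the PCR rule matches that restriction. That is a misnamed quantity in the protocol itself, not a detail left for later.

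A further objection is that the errors of 0.006–0.02 points cover surveillance prevalence only. This is correct. At 20% symptomatic prevalence and 98% specificity, the same formula is too high by 0.07 points at 85% sensitivity (1 − 0.016/0.83 = 98.07%) and 0.22 points at 50% (1 − 0.016/0.90 = 98.22%). These are still small, and the false-negative bound covers them.

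**Conclusion.** The concern holds: aim c is wrong as written and should be corrected before analysis. Together with the PCR rule it leads to a PPV, while the protocol promises specificity. Under the stated assumptions a 99%-specific card would be described by about 30–32% in surveillance at 0.5% prevalence and 90–91% in symptomatic testing at 10% prevalence. The prevalences and the 99% are illustrative. The dependence of the PPV on prevalence does not rest on them.

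The point does not extend to saying that specificity cannot be estimated. Because every positive is to be verified, specificity is recoverable to within about 0.02 percentage points for surveillance tests and about 0.2 points in the least favourable symptomatic case examined, taking saliva PCR as the reference. Sensitivity and negative predictive value are not identified by this design.

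**What to change.** Reword aim c to name two quantities:

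1. The PPV of BinaxNOW against PCR, TP/(TP + FP), reported separately for diagnostic tests in symptomatic subjects and surveillance tests in asymptomatic subjects.
2. The specificity of BinaxNOW, 1 − FP/(all valid tests − TP), with unverified card negatives counted as PCR-negative. State that assumption, give a bound for possible false negatives, and use an interval that allows for repeated tests within a subject. If specificity is also shown by symptom status, apply the bound within each group.

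Add a sentence that Step 1 does not estimate sensitivity or negative predictive value. The name of each quantity and its denominator belong in the aim; interval details can go in the SAP.

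The cost is one reworded aim, with no extra subjects, samples or laboratory tests. Specificity will rest on an explicit assumption whose effect is small. The separate PPVs will be imprecise, since only about 73–75 surveillance positives are expected at 0.5% prevalence, 99% specificity and full attendance.

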#### **B. Methods for STEP 1.**

240 students and 80 teachers/other school staff will be recruited from schools within the Madison Metropolitan School District. The schools will email families and teachers a letter explaining the study and inviting them to participate in a virtual information session which

includes a question answer opportunity. The virtual information sessions will describe the process of sample collection so that students and teachers know what to expect. If parents, teachers and other school staff are interested in enrolling in the study, they can contact the school at which time they will be asked if they agree to have study staff contact them. Research personnel will not directly contact parents, students, teachers or other school staff regarding initial recruitment for the study. All subjects will agree to the performance of nasal swabs samples to be used for diagnosis or screening. Samples will be obtained by research staff in the school setting. The Madison Metropolitan School District has obtained a CLIA waiver for collection of samples. When there is a positive test, a saliva sample will be collected for testing with a standard PCR method. The standard PCR samples will be processed at UW Clinical Laboratory.

All subjects will be followed for 8 weeks. Children and staff will not receive compensation for their participation in the study. Subjects are free to withdraw from the study at any time.

At the conclusion of this portion of the study, we will understand the feasibility and specificity of the testing procedures.

### **Data Collection:**

We will collect the following data elements from subjects; name, address, date of birth, and gender.

### **Confidentiality**

Electronic data will be stored in a password protected database on a password protected server. Subjects will receive a study ID. The key code linking the subject's name and study ID will be stored separately on the Department of Pediatrics password protected server and only available to research staff. Samples sent to the UW Clinical Laboratory will be labeled with the subject/study ID, date of birth and date of collection.

## **Reporting of test results**

Research personnel who are on site at the schools will report positive results from the BinaxNOW test to the subjects. School nurses will then notify parents of positive results immediately by phone and offer information about available resources, next steps and respond to questions.

In accordance with the Wisconsin Department of Health infectious disease reporting requirements, research staff will notify the local health office immediately with all positive results. In addition to the immediate report, research staff will complete and submit a case report form within 24 hours of a positive result.

The standard PCR samples that are processed at UW Clinical Laboratory will be labeled with a subject ID, date of birth and date of collection. The UW Clinical Laboratory will report positive test results to research staff who will then notify the school nurse.

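### Does a reporting sentence that names only positive PCR results leave the study unable to count BinaxNOW false positives for aim c?

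*Protocol*

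**What the plan says.** STEP 1 specific aim c, printed below the exclusion criteria in the Protocol, is to determine "The specificity of positive tests for SARS-CoV-2 obtained for diagnosis or surveillance compared to traditional PCR diagnostic testing". Section B (Methods for STEP 1) supplies the reference test: "When there is a positive test, a saliva sample will be collected for testing with a standard PCR method". The same section states that by the end "we will understand the feasibility and specificity of the testing procedures".

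The section on reporting of test results first covers BinaxNOW. Positives are reported to the subject, parents are telephoned by the school nurse, and the local health office is notified at once, with a case report form within 24 hours. It then turns to PCR: "The UW Clinical Laboratory will report positive test results to research staff who will then notify the school nurse". Nothing is said there, or elsewhere in the Protocol, about negative, invalid or missing PCR results.

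Three other statements bear on the point. On collection: "Samples will be obtained by research staff in the school setting". On identification: "Samples sent to the UW Clinical Laboratory will be labeled with the subject/study ID, date of birth and date of collection". On data: "We will collect the following data elements from subjects; name, address, date of birth, and gender".

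**The concern.** Because saliva PCR is described only after a positive test, a negative PCR result is the record of a BinaxNOW false positive. If the laboratory sent back positives alone and the analysis used only what came back, every returned result would confirm BinaxNOW and the false-positive count would be zero by construction. If a missing report were instead taken as a negative, samples that were lost, insufficient or still pending would be counted as false positives. Either way, one of the three aims of STEP 1 would rest on a defective reference standard.

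There is a second worry. Families hear of a BinaxNOW positive at once, and the Protocol does not say that anyone tells them when PCR fails to confirm it, although school attendance is among its stated goals.

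**Working it through.** The Protocol gives no target specificity, precision or power, so there is no stated figure to reproduce. The check has two parts.

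**1. What the text fixes**

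- The PCR sentence names positives. It contains no word limiting the laboratory to positives and no instruction to hold back negatives.
- The BinaxNOW sentence in the same section also speaks only of positive results. Nobody would conclude from it that BinaxNOW negatives go unrecorded. The PCR sentence likewise ends with onward notice to the school nurse, so both read as notification rules.
- The data collection list contains no test result of any kind, not even BinaxNOW. The Protocol leaves results capture undescribed throughout, so silence on PCR negatives carries no special meaning.
- Research staff know every BinaxNOW positive, because they report each one to the subject and to the health office. They also take the samples, which reach the laboratory under a study ID. Hence, even if only positives came back: unconfirmed positives = saliva samples sent − PCR positives reported. A sample that was never taken is known to the staff who did not take it. Only lost, invalid or pending samples remain mixed with true negatives.

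**2. How much the remaining ambiguity could matter**

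Inputs from the Protocol: 240 + 80 = 320 subjects, 8 weeks, two surveillance tests a week, and sensitivity of 85% (the low end of the 85 to 95% given in the Background). Full adherence gives 320 × 8 × 2 = 5,120 tests. Prevalence per test and specificity are assumptions, because the Protocol gives neither.

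Formulas, with N = 5,120, prevalence p, sensitivity Se and specificity Sp:

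- TP = N·p·Se and FP = N·(1 − p)·(1 − Sp)
- confirmed share = TP / (TP + FP)
- if 10% of true positives have no PCR result and are counted as false positives, the confirmed share becomes 0.9·TP / (TP + FP), and specificity becomes (TN + FN) / (TN + FN + FP + 0.1·TP), taking BinaxNOW negatives as uninfected

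At p = 0.2%, Sp = 99.5%:

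- TP = 5,120 × 0.002 × 0.85 = 8.7 and FP = 5,120 × 0.998 × 0.005 = 25.5
- share of positives that are false = 25.5 / 34.2 = 75%, so the confirmed share is about 25%

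Over p of 0.1 to 0.5%, Sp of 99.5 to 99.9% and Se of 85 to 95%, the false share runs from 17% to 85%. This is the share of BinaxNOW positives whose PCR return is not described. It is not a bias.

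Bias under the subtraction rule with 10% of true positives lacking a PCR result (Se = 85%):

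| Prevalence | True Sp | TP | FP | Sp estimated | Confirmed share, true → estimated |
|---|---|---|---|---|---|
| 0.1% | 99.9% | 4.4 | 5.1 | 0.9989 | 0.460 → 0.414 |
| 0.5% | 99.5% | 21.8 | 25.5 | 0.9946 | 0.461 → 0.415 |
| 1% | 99% | 43.5 | 50.7 | 0.9892 | 0.462 → 0.416 |
| 1% | 98% | 43.5 | 101.4 | 0.9792 | 0.300 → 0.270 |

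Across prevalence 0.1 to 1% and specificity 98 to 99.9%, the loss in specificity stays below 0.1 percentage point. The confirmed share always falls by one tenth of its value.

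**The case for a change.** The strongest case for a change is that the sentence has two legs. The second, from staff to nurse, is notification. The first, from laboratory to research staff, is the only described way for a PCR result to reach the study. The parallel with BinaxNOW is therefore imperfect: those tests are carried out at the school with research personnel present, whereas for PCR the laboratory is the only source. An analysis plan cannot recover a result that was never sent, and a study should not have to infer a main outcome from silence. Aim c is also worded in terms of positive tests, so the confirmed share may be the quantity most directly in view, and a one-tenth loss there is less trivial than the loss in specificity.

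Part of this stands. No route is written for negative, invalid or missing PCR results, and subtraction cannot separate a true negative from a lost sample. What does not stand is the step from silence to prohibition. A contrast of 100% apparent against 25% true confirmation arises only if an analyst discards every sample without a positive report, and the Protocol proposes no such analysis. The point about families is also drawn from silence: nothing bars telling them, and the nurses are already assigned to answer parents' questions after a positive.

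**Conclusion.** The concern does not call for a change. The Protocol says how positive PCR results are passed on and leaves the rest of the results handling unwritten. It does not withhold negatives, and aim c remains estimable as far as this sentence is concerned. A team that sends ID-labelled samples for the purpose of computing specificity will ask for all the results, and the treatment of invalid or missing ones is commonly settled in the analysis plan, which is not at hand. Even under a strict positives-only reading, with 10% of true positives lacking a result, the effect is under 0.1 percentage point of specificity and a tenth of the confirmed share.

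These sizes assume full adherence (5,120 tests), 85% sensitivity, prevalence of 0.1 to 1% and specificity of 98 to 99.9%, and they scale with the fraction of results missing. They also take BinaxNOW negatives as uninfected. That PCR follows only a positive test is a separate matter, which returning every PCR result would not alter.
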